often adult children or spouses. Perpetrators are likely to be male, socially isolated, unemployed, have substance abuse, mental or physical health problems, a police record, or financial problems. Mistreatment victims have high rates of depressive symptoms. Victims of EM have one of the highest rates of depression among older adults (<http://www.aoa.acl.gov/>). A population-based study found that mistreatment victims had significantly higher rates of depressive symptoms (31.6% vs. 6.8%) and suicidal ideation (16.4% vs. 3.4%) than non-mistreated older adults. In a 7.6 year follow-up of an urban sample, adults with concurrent mistreatment and depressive symptoms had higher rates of mortality than non-depressed victims of mistreatment. In our own work in NYC, 34% of victims endorsed significant depressive symptoms and 16% reported suicidal ideation. Consistent with our Center's deployment focused model, EM/PROTECT has been developed through an iterative process with the NYC DFTA Elderly Crime Victim Resource Center (ECVRC). EM aims to install protection measures, while PROTECT targets the behavioral Page 23 of 34 5/9/19 1:02 PM consequences of stress on the CCN and the reward networks thus reducing the experience of stress.

## STUDY DESIGN

EM/PROTECT, a behavioral intervention for depressed elder mistreatment (EM) victims, was designed to work in synergy with EM mistreatment resolution services that provide safety planning, support services, and links to legal services. PROTECT is built on a model which postulates that chronic stress promotes dysfunction of the cognitive control (CCN) and reward networks, impairing the victims' ability to flexibly respond to the environment and limits their rewarding activities. PROTECT therapists work with EM victims to develop action plans to reduce stress, and to increase rewarding experiences. EM/PROTECT has been designed in an iterative process with community EM providers of the New York City (NYC) Dept. for Aging (DFTA) to use agencies' routine depression screening and referral for service. We propose to collect data on feasibility and acceptability of EM/PROTECT. We will compare the effectiveness and target engagement of EM/PROTECT with EM enriched with training of EM staff in linking EM victims to mental health services (EM/MH) in order to position us for a fully powered R01. To ensure rigor and reproducibility, EM/PROTECT or EM/MH will be offered to randomly assigned depressed EM victims, and standardized assessments will be conducted by trained raters blind to participant assignment and our hypotheses. The training of staff and therapists will follow high standards of intervention fidelity. EM staff will screen using routine standardized measures and refer depressed victims to study staff who will describe the study and obtain consent and conduct research assessments. We will use brief validated instruments to assess the outcomes, explore the added value of mobile technology measures, and study the effect of sex in each aim. The EM agencies of NYC are overseen and funded by DFTA. We will Page 22 of 34 5/9/19 1:02 PM begin by working with the Elderly Crime Victims Resource Center (ECVRC), as we have successfully partnered with them in the past for our initial exploratory work ([name] et al., 2015a and b). We will then work with DFTA to identify a second site. At both sites we will provide refresher training in depression screening and strategies for linking victims to mental health using the Open Door approach we jointly developed with DFTA. Randomization at the participant level will be conducted by the Methods Core (random numbers in blocks of varying size). Both agencies will conduct depression screening. EM workers will not be blind to treatment arm. We are aware that their knowledge of treatment assignment may influence the EM services they provide. For this reason, we will record and compare their services between the two treatment arms to inform the design of the R01 proposal that will follow this R34 study.

The primary objective of the EM/PROTECT project will be to evaluate the effectiveness of EM/PROTECT compared to EM/MH. We also propose to examine the reach, feasibility, and acceptability of EM/PROTECT for depressed EM victims. 1) Effectiveness: In both conditions, the reduction of clinically significant depressive symptoms (as measured on the Montgomery Asberg Depression Rating Scale [MADRS]) and improved quality of life. 2) Reach: In both conditions, number of clients screened vs. all eligible for screening, and clients who meet study criteria. 3) Feasibility: Number of victims who initiate EM/PROTECT, number of EM/MH victims who make contact with mental health services, number who attend research procedures. EM/PROTECT: session completion rate; smartphone use. 4) Acceptability: Victims satisfaction (CSQ) in both treatments; EM/PROTECT session completion at 6, 9, 12, and 16 weeks.

We plan to recruit 4.5 subjects per month over 14 months to achieve a final sample of 80 subjects. We will recruit 2 licensed clinical social workers to administer the PROTECT therapy sessions with clients. The larger number of EM/PROTECT participants will allow a better view of effectiveness and reach/feasibility/acceptability. Effectiveness objective: In separate linear mixed models, we will analyze primary (MADRS, WHOQOL assessed at baseline, 6, 9 and 12 weeks) and secondary measures of effectiveness (PAM, ratings of mood and anhedonia assessed daily) with a subject-specific random intercept and slope and fixed effects for time, treatment, EM agency, LCSW, treatment x time interaction. We will use model building and fitting strategies. In the final model, we will also estimate end of treatment improvements in outcome (from baseline) within each treatment group. As Page 24 of 34 5/9/19 1:02 PM this is an inadequately powered R34 study, we will control for false discovery rate using the Benjamini-Hochberg approach, and not the Family-Wise Error Rate, to adjust for multiple comparisons of secondary outcomes. The focus of our analysis would be to obtain preliminary signals of effectiveness by estimating effect sizes (95% CI) and assessing clinical relevance. Using approaches of Initiative 2.1 (Methods Core), we will conduct exploratory joint analysis of primary and secondary longitudinal outcomes. We will also test between group differences in smartphone measures using the time series approach of Initiative 2.1 (Methods Core). Reach/feasibility/acceptability objective: We will calculate estimates and 95% CI of the following measures for all subjects and for each sex separately. Reach: Proportions screened and met study criteria in both conditions. Feasibility: Among EM/PROTECT clients, proportions of: treatment drop-outs, assessment completions, smartphone use. Proportion of EM/MH victims who contacted mental health services. Acceptability by clients: We will analyze victim satisfaction (CSQ) recorded at baseline, 6, 9, 12 and 16 weeks as in Aim 4. Benchmark tests of feasibility (75% session attendance rate and 70% smartphone ratings) and acceptability will be performed using one-sample z-test of proportions.

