PROTOCOL TITLE: EM/PROTECT: Improving Depression in Elder Mistreatment Victims

PRINCIPAL INVESTIGATOR: [name] [name], PhD, Weill Cornell Medicine

IRB Protocol #: 1703018101

ClinicalTrials.gov Identifier: NCT03241225

Current Version: November 24, 2021

Descriptive statistics for continuous (median and interquartile range; IQR) and categorical (frequency and percentage) were reported on demographics and clinical characteristics of two treatment groups at baseline. A Mann-Whitney test and Fisher's exact test were conducted to test the difference between PROTECT and Usual care for continuous and categorical variables, respectively.

Remission rate was defined as the percentage of participants with MADRS scores  $\leq 10$  at Week 9. Response was defined as a reduction of  $\geq 50\%$  in MADRS scores from baseline to Week 9. We conducted two mixed-effects linear regression models to compare the trajectories of change in MADRS scores and WHOQOL scores between PROTECT and Usual care, respectively. Each model included fixed effects of treatment (PROTECT vs. Usual care), time, and their interaction, as well as a participant-specific random intercept. Both models were adjusted for age and gender. Site and its interaction with treatment were initially included in the model but were dropped as their effects were statistically non-significant. A two-sided p-value less than 0.05 was considered statistically significant. Intent-to-treat analyses are presented with all available data in the mixed-effects models. Remission and response rates were calculated based on 30 patients with complete data. All analyses were conducted in R 3.6.1 (R Foundation for Statistical Computing; <http://www.r-project.org/>).

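### No stratification by agency is described for the blocked randomisation, and the SAP drops site on a significance test: a small, cheaply avoided loss of precision

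*Protocol*

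**What the plan says.** The design paragraph of the protocol (STUDY DESIGN) describes participant-level allocation by the Methods Core using "random numbers in blocks of varying size". It gives no stratification factor, number of lists, block sizes or numerical ratio. Recruitment starts at one agency, and of the other it says: "We will then work with DFTA to identify a second site". Neither that agency's opening date nor its share of recruitment is given.

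The statistical paragraph under the same heading lists the planned model terms as "fixed effects for time, treatment, EM agency, LCSW, treatment x time interaction". It also refers to a larger number of participants in EM/PROTECT, which suggests unequal allocation, and it concedes that the study lacks adequate power.

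The SAP reports a different final model: "Site and its interaction with treatment were initially included in the model but were dropped as their effects were statistically non-significant". What it kept is stated separately: "Both models were adjusted for age and gender".

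**The concern.** Each agency delivers the background mistreatment services, so change in MADRS could differ between agencies. Including agency in the planned model shows that the protocol allows for this. Blocks on a shared list balance the total, not each agency. If the arms then differ in their agency mix, any agency difference in outcome enters the treatment estimate as noise unless the model removes it. The SAP models do not. A non-significant site test in a small study is weak evidence that site can be ignored. At stake is the precision of the effect-size estimates that are meant to inform a later, fully powered trial.

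**Working it through.** **The plan's own figures.** The documents give no figure for site balance, effect size, SD or power. The only design figure that can be checked is the sample size: 4.5 per month × 14 months = 63, not the stated 80. That is a separate matter, but it is why both 80 and 63 are used below.

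**Assumptions (not in the documents).** Ratio 1:1, 3:2 or 2:1. Block sizes 4/6 or 2/4/6 (1:1), 5/10 (3:2) and 3/6 (2:1). Second agency contributing 20, 30 or 40 of 80.

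**Step 1: site imbalance.** Let d be the difference between arms in the share of participants from the second agency. If recruitment overlaps fully on one list, SD(d) = √[p(1−p)(1/n₁ + 1/n₀) × N/(N−1)]. With p = 20/80 and 40 per arm: √[0.1875 × 0.05 × 80/79] = √0.00949 = 0.097, and 1.96 × 0.097 = 0.19. Simulation of the same case gives a 95th percentile of 0.20, the gap being due to the coarse scale of d.

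Simulated 95th percentiles of |d|, N = 80:

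| Setting | One list, overlapping | One list, second agency only after the first | Separate lists |
|---|---|---|---|
| 20 at agency 2, entering after the first 30; 1:1 | 0.16 | 0.05 | 0.04 |
| 30 at agency 2, entering after the first 20; 1:1 | 0.20 | 0.05 | 0.03 |
| The same two settings; 3:2 and 2:1 | 0.16 to 0.21 | 0.05 to 0.07 | 0.03 to 0.04 |
| 20 or 40 at agency 2, full or partial overlap; 1:1 to 2:1 | 0.17 to 0.23 | 0.05 to 0.07 | 0.03 to 0.04 |

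In the first setting a shared list gives 13:7 or worse at the second agency in about 16% of trials and 14:6 or worse in about 4.5%. Separate lists gave neither. Across the grid in the last row, the chance that |d| exceeds 0.10 is 19% to 49% with overlap (32% to 44% at N = 63). It is 0% to 2% if the agencies recruit in sequence (up to 9.5% at N = 63), and at most 1.5% with separate lists.

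**Step 2: effect on the estimate.** Assume the agencies differ by 3 points in MADRS change and the SD of change is 8.

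- Standard error without site imbalance, 40 per arm: 8 × √(1/40 + 1/40) = 1.789.
- A 95th percentile of 0.163 implies SD(d) ≈ 0.163/1.96 = 0.083, so the added error has SD 3 × 0.083 = 0.25 points.
- Combined: √(1.789² + 0.25²) = 1.806, a rise of about 1.0%.
- Upper end, 2:1 with a 95th percentile of 0.21: 8 × √(1/53.3 + 1/26.7) = 1.897; 3 × 0.21/1.96 = 0.32; √(1.897² + 0.32²) = 1.924, a rise of about 1.4%.
- Separate lists, 95th percentile 0.04: 3 × 0.04/1.96 = 0.06; √(1.789² + 0.06²) = 1.790, a rise below 0.1%.

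The 95th percentile of the error itself is 3 × 0.16 = 0.5 to 3 × 0.20 = 0.6 points on a shared list at 1:1, against about 3 × 0.04 = 0.1 with separate lists.

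**Step 3: adjusting instead of stratifying.** In a linear model with site as a covariate, the variance of the treatment effect is multiplied by 1/(1 − r²), where r is the correlation between arm and site. With overlap its mean excess is 0.9% to 1.3% at N = 80 and 1.2% to 1.7% at N = 63.

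**The case against.** The strongest reply is that the text does not establish a shared list. It is silent on stratification, the protocol is available only in part, and the Methods Core may hold a list per agency. That stands: a reader might infer that one unstratified list was used, but the documents show only that stratification is not described.

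A reader might also infer that the later opening of the second agency causes the imbalance. It does not. Blocks run over time, so recruitment in sequence is nearly balanced by agency already. Overlap is what creates the imbalance, and its extent is not given. The protocol does refer to both sites and both agencies, and nothing says that the first one closes.

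Nor is this bias. Imbalance under randomisation is a chance event, and the loss is slight in a pilot that seeks preliminary signals. The 3-point effect and the SD of 8 have no source in the documents. The protocol's own model, with agency as a fixed effect, already offers a remedy, and dropping that term is an analysis decision that does not show the randomisation to be faulty. No within-agency treatment comparison is planned that would be damaged. All of this stands, and it limits the point to a minor one.

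Finally, a shared list is not without merit. It is simpler, and agency staff, who screen, refer and are not blind to arm, could guess the next assignment a little more easily from an agency's own sequence. This carries limited weight: block sizes vary, and until the second agency opens the sequence belongs to one agency in any case.

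**Conclusion.** The point holds as a minor one. The protocol names no stratification by agency while planning agency as a model term, and the SAP's final models omit site because of a non-significant test. If one list was used with overlapping recruitment, a noticeable chance imbalance by agency is likely: 95th percentile about 0.16 to 0.21, and up to 0.23 over a wider set of assumptions, against 0.03 to 0.04 with separate lists. The resulting loss is about 1% in the standard error under the assumed 3-point effect and SD of 8, and scarcely anything if the agencies recruited in sequence. These figures rest on assumed ratios, block sizes, site shares and timing, and on 80 participants. The SAP mentions 30 with complete data and gives no number randomised. The documents do not support a finding of bias, of defective randomisation, or of a design choice with nothing in its favour.

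**What to change.** 1. Generate a separate varying-block list for each agency at the intended allocation ratio, and state both the stratification and the ratio in the design paragraph of the protocol. If this was already done, say so.
2. Keep agency in the final MADRS and WHOQOL models whatever its p-value. This is right whether or not the lists were separate. A main effect corrects only for differences in level; if the agencies may differ in change over time, an agency-by-time term is needed too.
3. Report the number randomised by arm and agency.

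The SAP is written in the past tense. If allocation is complete, items 2 and 3 remain available and item 1 becomes a statement of what was done and a design choice for the later trial.

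Cost: one extra list for the Methods Core and no extra participants. Each agency may end with one incomplete block, leaving the total off its ratio by a few participants, and assignments within an agency become slightly more predictable, which varying block sizes limit. The extra model terms cost one or a few degrees of freedom.

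### The recruitment figures disagree: 4.5 subjects per month for 14 months gives 63, not the stated 80

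*Protocol*

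**What the plan says.** The Protocol's STUDY DESIGN section gives the rate, the period and the total in one sentence: "We plan to recruit 4.5 subjects per month over 14 months to achieve a final sample of 80 subjects".

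Three other statements in that section bear on how to read it:

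- **Sites.** Work starts at one agency. For the next, the text says only "We will then work with DFTA to identify a second site". It gives no start date and no rate for that site.
- **Allocation.** The arms are unequal: "The larger number of EM/PROTECT participants will allow a better view of effectiveness and reach/feasibility/acceptability". The ratio is not given, but it does not affect the total.
- **Power.** The Protocol says "this is an inadequately powered R34 study" and shows no sample size calculation, so 80 has no derivation other than the recruitment sentence.

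The SAP states no planned sample size. It mentions 30 patients only as the number with complete data for the remission and response rates.

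**The concern.** The sentence presents 80 as what the stated rate and period will produce, and multiplying the two does not give 80.

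The number matters because the Protocol makes estimation its main purpose. Effect sizes are to be reported with 95% confidence intervals and judged for clinical relevance. Reach, feasibility and acceptability are also to be estimated with intervals, overall and for each sex. The planned precision of all of these depends on the number of subjects.

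The study is also meant to prepare a fully powered successor. A reader planning that trial cannot tell whether the intended pace was 4.5 or about 5.7 subjects per month, or whether the intended period was 14 or about 18 months.

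**Working it through.** **Inputs (Protocol, STUDY DESIGN)**

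- Rate: 4.5 subjects per month
- Period: 14 months
- Stated final sample: 80

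**Attempt to reproduce the stated figure**

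Accrual = rate × months = 4.5 × 14 = 63.

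Shortfall = 80 − 63 = 17, and 17 / 80 = 21.25%. The stated 80 is not reproduced.

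**Readings that might recover 80**

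| Reading | Calculation | Result |
|---|---|---|
| Inputs rounded to the last digit shown | 4.45 × 13.5 to 4.549 × 14.5 | 60.1 to 66.0 |
| Looser rounding (rate to the nearest half, period to the nearest month) | 4.75 × 14.5 | 68.9; still 11.1 short (13.9%) |
| Rate is per site, two sites for the full period | 2 × 4.5 × 14 | 126 |
| Rate is per site, second site opens late | 17 / 4.5 | 3.8 months at the second site would be needed |
| 80 is the number left after dropout (assumed 10% or 20%) | 80 / 0.9 or 80 / 0.8 | 89 or 100 recruits needed; the gap widens |
| 63 complete out of about 80 recruited (assumed 20% dropout) | 63 / 0.8 | 79 |

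The last row comes close, but it reverses the sentence, which attaches 4.5 per month to recruitment and 80 to the final sample. The dropout rates in the table are assumptions; the documents state none. The late second site also reaches 80, but only on an assumed per-site rate and an assumed opening time.

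**What would make the figures agree**

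- Keep 80 and 14 months: 80 / 14 = 5.71 per month, and 5.71 / 4.5 = 1.27, a rate about 27% higher. Check: 5.7 × 14 = 79.8.
- Keep 80 and 4.5 per month: 80 / 4.5 = 17.8 months, about 3.8 months longer. Check: 4.5 × 18 = 81.
- Keep 4.5 per month and 14 months: 63 subjects.

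**Effect on precision, only if the planned number is really 63**

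At any fixed allocation ratio, the width of a confidence interval is approximately proportional to 1/√N. The ratio of widths is √(80/63) = 1.127, so intervals would be about 13% wider than with 80.

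**The case against.** The strongest defence is the staged opening of sites. If 4.5 per month is the rate at one agency, under four months of recruitment at the second would supply the missing 17. The rate would then be under-described rather than wrong. The public Protocol is also an extract: its page footers place this text at pages 22 to 24 of 34. The lack of a bridging statement is therefore weak evidence that none was ever written. This stands as a possibility. It does not make the sentence correct, because the sentence gives a single rate, period and total and does not call the rate per-site.

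The second argument is that little follows from the error. The number 80 is not derived from power or precision, and no visible calculation, decision rule or analysis uses 4.5 or 14. Nothing says that recruitment closes at 14 months regardless of the number reached. The SAP, dated November 2021, reports analyses already done, so correcting a forecast changes no result. All of this stands. It limits the severity of the point, and it means the 13% is conditional and not a loss that the error is known to have caused.

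A dropout defence fails on the wording: if 80 is the number remaining, more than 80 must be recruited.

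**Conclusion.** The concern holds, as a minor one. As written, the stated rate and period deliver 63 subjects, 17 (21%) fewer than the stated 80, and no reasonable rounding closes the gap.

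The arithmetic uses only the figures in that sentence. It assumes that 4.5 is the overall monthly rate, as the wording implies. The documents do not show which of the three figures is wrong, although 80 is clearly the number the sentence aims for.

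No power or inferential claim fails. If 80 is right, the loss of precision is zero and only the recruitment schedule is misstated.

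**What to change.** Rewrite the recruitment sentence so that its three figures agree, using whichever of these matches what was intended:

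- restate the expected sample as 63;
- keep 80 and restate the rate as about 5.7 per month, or the period as about 18 months;
- if 4.5 is a per-site rate, say so and give the second site's recruitment period (about 3.8 months would reach 80).

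The sponsor must say which applies; the documents do not settle it. The cost is one corrected sentence, with no change to the design or the analysis model. Since the SAP describes completed analyses, the change repairs the record of the plan and does not alter the precision obtained.

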#### INCLUSION AND EXCLUSION CRITERIA

Inclusion Criteria: 1) 55 years of age or older 2) capacity to consent (per EM staff) 3) significant depression (per EM staff) as indicated by a score of 10 or above on the Patient Health Questionnaire-9 (PHQ-9), a widely used screening tool routinely administered in EM agency settings (the PHQ-9 has a sensitivity of 88% and a specificity of 88% for major depression) 4) need for EM services.

Exclusion Criteria: 1) Active suicidal ideation (MADRS item 10 >4) 2) inability to speak English 3) Axis 1 DSM-5 diagnoses other than unipolar depression or generalized anxiety disorder (by SCID) 4) MOCA

score of 23 or less 5) Severe or life-threatening medical illness 6) EM emergency and or referral out of EM agency (per EM staff

